15.1.2. Serious Adverse Event

An SAE is any untoward medical occurrence that at any dose:

- Results in death
- In the view of the Investigator, places the subject at immediate risk of death (a life-threatening event); however, this does not include an event that, had it occurred in a more severe form, might have caused death
- Requires inpatient hospitalization or prolongation of existing hospitalization
- Results in persistent or significant disability/incapacity

CONFIDENTIAL

The information contained herein may not be used, disclosed, or published without the written consent of Biogen MA Inc.

- Results in a congenital anomaly/birth defect
- Is a medically important event

A medically important event is an AE that, in the opinion of the Investigator, may jeopardize the subject or may require intervention to prevent one of the other outcomes listed in the definition above. (Examples of such medical events include allergic bronchospasm requiring intensive treatment in an emergency room or convulsions occurring at home that do not require an inpatient hospitalization.)

15.1.3. Prescheduled or Elective Procedures or Routinely Scheduled Treatments

A prescheduled or elective procedure or a routinely scheduled preventative health procedure (e.g., colonoscopy) will not be considered an SAE, even if the subject is hospitalized. The study site must document all of the following:

- The prescheduled or elective procedure or routinely scheduled treatment was scheduled (or was on a waiting list to be scheduled) prior to obtaining the subject's consent to participate in the study.
- The condition requiring the prescheduled or elective procedure or routinely scheduled treatment was present before and did not worsen or progress in the opinion of the Investigator between the subject's consent to participate in the study and the time of the procedure or treatment.
- The prescheduled or elective procedure or routinely scheduled treatment is the sole reason for the intervention or hospital admission.
 - If a subject is hospitalized due to local requirements for administration of the study treatment, the hospitalization should not be considered an SAE unless one of the requirements in Section 15.1.2 is met.

15.2. Safety Classifications

15.2.1. Investigator Assessment of Events

All events must be assessed to determine the following:

- If the event meets the criteria for an SAE as defined in Section 15.1.2 .
- The relationship of the event to study treatment as defined in Section 15.2.2
- The severity of the event as defined in Section 15.2.3.

CONFIDENTIAL

The information contained herein may not be used, disclosed, or published without the written consent of Biogen MA Inc.

15.2.2. Relationship of Events to Study Treatment

The following definitions should be considered when evaluating the relationship of AEs and SAEs to the study treatment.

Relationship of Event to Study Treatment	
Not related	An AE will be considered “not related” to the use of the investigational product if there is not a reasonable possibility that the event has been caused by the product under investigation. Factors pointing toward this assessment include but are not limited to the lack of reasonable temporal relationship between administration of the investigational product and the AE, the presence of a biologically implausible relationship between the product and the AE, or the presence of a more likely alternative explanation for the AE.
Related	An AE will be considered “related” to the use of the investigational product if there is a reasonable possibility that the event may have been caused by the product under investigation. Factors that point toward this assessment include but are not limited to a positive rechallenge, a reasonable temporal sequence between administration of the investigational product and the AE, a known response pattern of the suspected product, improvement following discontinuation or dose reduction, a biologically plausible relationship between the product and the AE, or a lack of an alternative explanation for the AE.

15.2.3. Severity of Events

The following definitions should be considered when evaluating the severity of AEs and SAEs:

Severity of Event	
Mild	Symptoms barely noticeable to subject or does not make subject uncomfortable; does not influence performance or functioning; prescription drug not ordinarily needed for relief of symptoms but may be given because of personality of subject.
Moderate	Symptoms of a sufficient severity to make subject uncomfortable; performance of daily activity is influenced; subject is able to continue in study; treatment for symptoms may be needed.
Severe	Symptoms cause severe discomfort; symptoms cause incapacitation or significant impact on subject’s daily life; severity may cause cessation of treatment with study treatment; treatment for symptoms may be given and/or subject hospitalized.

15.2.4. Expectedness of Events

Expectedness of all AEs will be determined by the Sponsor according to the Investigator’s Brochure.

15.3. Monitoring and Recording Events

15.3.1. Adverse Events

Any AE (including SAEs) experienced by the subject between the time of first dose of study treatment and the subject’s last study visit is to be recorded on the CRF, regardless of the severity of the event or its relationship to study treatment. At each study visit, the Investigator

CONFIDENTIAL

The information contained herein may not be used, disclosed, or published without the written consent of Biogen MA Inc.

will assess the subject for AEs and will record any new AEs or updates to previously reported AEs on the CRF.

AE outcome will be recorded on the CRF, as applicable.

Expected fluctuations or expected deterioration of the underlying IPF and other pre-existing conditions should not be recorded as an AE except in the following circumstances:

- Worsening of the disease meets the criteria for an SAE.
- Action is taken with investigational treatment, such as when treatment is discontinued.
- Additional treatment is required, such as when concomitant medication is added or changed.
- In the opinion of the Investigator, an unexpected deterioration from baseline has occurred.
- The event meets the criteria of an acute exacerbation of IPF.

15.3.2. Serious Adverse Events

Any SAE experienced by the subject between the time of the signing of the ICF and the subject's last study visit is to be recorded on an SAE form, regardless of the severity of the event or its relationship to study treatment. SAEs must be reported to the Sponsor within 24 hours as described in Section 15.3.3. Follow-up information regarding an SAE also must be reported within 24 hours. See the Study Reference Guide's Official Study Contact List for complete contact information.

Subjects will be followed for all SAEs until their last study visit. Thereafter, the event should be reported to the Sponsor only if the Investigator considers the SAE to be related to study treatment.

SAEs that are ongoing when the subject completes or discontinues the study will be followed by the Investigator until the event has resolved, stabilized, or returned to baseline status. SAE outcome will be recorded on the CRF, as applicable. Only SAEs that are unresolved will be followed by the Investigator.

15.3.3. Immediate Reporting of Serious Adverse Events

In order to adhere to all applicable laws and regulations for reporting an SAE, the study site must formally notify the Sponsor within 24 hours of the study site staff becoming aware of the SAE. It is the Investigator's responsibility to ensure that the SAE reporting information and procedures are used and followed appropriately.

CONFIDENTIAL

The information contained herein may not be used, disclosed, or published without the written consent of Biogen MA Inc.

Reporting Information for SAEs

A report **must be submitted** to the Sponsor regardless of the following:

- Whether or not the subject has undergone study-related procedures
- Whether or not the subject has received study treatment
- The severity of the event
- The relationship of the event to study treatment

To report initial or follow-up information on an SAE, a completed SAE form must be sent to the Sponsor; refer to the Study Reference Guide's Official Study Contact List for complete contact information.

15.3.3.1. Deaths

Death is an outcome of an event. The event that resulted in death should be recorded on the appropriate CRF. All causes of death must be reported as SAEs within 24 hours of the site becoming aware of the event. The Investigator should make every effort to obtain and send death certificates and autopsy reports to the Sponsor. The term death should be reported as an SAE only if the cause of death is not known and cannot be determined.

15.3.4. Suspected Unexpected Serious Adverse Reactions

Suspected unexpected serious adverse reactions (SUSARs) are SAEs that are unexpected and judged by the Investigator or the Sponsor to be related to the study treatment administered.

Appropriate personnel at the Sponsor will unblind SUSARs for the purpose of regulatory reporting. The Sponsor will submit SUSARs (in blinded or unblinded fashion) to regulatory agencies according to local law. The Sponsor will submit SUSARs to Investigators in a blinded fashion.

15.4. Procedures for Handling Special Situations

15.4.1. Pregnancy

Subjects should not become pregnant or impregnate their partners during the study and for 3 months after their last dose of study treatment. If a female subject becomes pregnant, study treatment must be discontinued *immediately*.

The Investigator must report a pregnancy occurring in a female subject from first dose of study treatment up to 3 months after the last dose by faxing or emailing the appropriate form to the Sponsor within 24 hours of the study site staff becoming aware of the pregnancy. Refer to the Study Reference Guide's Official Study Contact List for complete contact information. The

CONFIDENTIAL

The information contained herein may not be used, disclosed, or published without the written consent of Biogen MA Inc.

Investigator or study site staff must report the outcome of the pregnancy to the Sponsor. A pregnancy is not considered an AE and should not be recorded on the AE CRF.

Congenital abnormalities and birth defects in the offspring of male or female subjects should be reported as SAEs if conception occurred during the study treatment period.

15.4.2. Overdose

An overdose is any dose of study treatment administered to a subject or taken by a subject that exceeds the dose assigned to the subject according to the protocol. A window of +2 days is allowed without qualifying as an overdose for non-Baseline Visits; however, subsequent doses should adhere to the dosing schedule initiated at the Baseline Visit. Overdoses are not considered AEs and should not be recorded as an AE on the CRF; however, all overdoses must be recorded on an Overdose form and faxed or emailed to the Sponsor within 24 hours of the site becoming aware of the overdose. An overdose must be reported to the Sponsor even if the overdose does not result in an AE. If an overdose results in an AE, the AE must be recorded. If an overdose results in an SAE, both the SAE and Overdose forms must be completed and faxed or emailed to the Sponsor. All study treatment-related dosing information must be recorded on the dosing CRF.

15.4.3. Medical Emergency

In a medical emergency requiring immediate attention, study site staff will apply appropriate medical intervention, according to current standards of care. The Investigator should contact the study's Medical Director. Refer to the Study Reference Guide's Official Study Contact List for complete contact information.

15.4.3.1. Unblinding for Medical Emergency

In a medical emergency when knowledge of the subject's treatment assignment may influence the subject's clinical care, the Investigator may access the subject's treatment assignment by IRT. The Investigator must document the reasons for unblinding in the subject's source documents. The Investigator is strongly advised not to divulge the subject's treatment assignment to any individual not directly involved in managing the medical emergency, or to personnel involved with the analysis and conduct of the study. The Investigator can contact the Sponsor to discuss such situations.

15.5. Contraception Requirements

All women of childbearing potential and all men must practice highly effective contraception during the study. Women in the study (and/or their partner) must continue highly effective contraception and must not donate eggs for 3 months after stopping study treatment. Men in the study (and/or their partner) must continue effective contraception and must not donate sperm for 4 months after stopping study treatment.

CONFIDENTIAL

The information contained herein may not be used, disclosed, or published without the written consent of Biogen MA Inc.

For the purposes of this study, women who do not meet one of the following criteria are considered to be physiologically capable of becoming pregnant and are, therefore, defined as women of childbearing potential:

- Postmenopausal
 - 12 continuous months of natural (spontaneous) amenorrhea without an alternative medical cause.
 - 6 weeks after surgical bilateral oophorectomy with or without hysterectomy
- Posthysterectomy
- Female surgical sterilization (e.g., bilateral tubal ligation)

For the purposes of the study, highly effective contraception is defined as use of 1 of the following:

For females:

- Established use of oral, intravaginal, or transdermal combined (estrogen and progestogen containing) hormonal methods of contraception associated with the inhibition of ovulation.
- Established use of oral, injected, or implanted progestogen-only hormonal methods of contraception.
- Placement of an intrauterine device or intrauterine hormone-releasing system.
- Sex with a male who has undergone surgical sterilization (with the appropriate postvasectomy documentation of the absence of sperm in the ejaculate).

For males:

- Vasectomy (with the appropriate postvasectomy documentation of the absence of sperm in the ejaculate).
- Sex with a woman who uses the methods described for females if she is of childbearing potential.

True abstinence, when this is consistent with the preferred and usual lifestyle of the subject, can be considered an acceptable method of contraception based on the evaluation of the Investigator who should also take into consideration the duration of the clinical trial. Periodic abstinence (e.g., calendar, ovulation, symptothermal, postovulation methods) and withdrawal are not considered acceptable methods of contraception.

Pregnancy reporting is described in Section [15.4.1](#).

CONFIDENTIAL

15.6. Safety Responsibilities

15.6.1. The Investigator

The Investigator's responsibilities include the following:

- Monitor and record all AEs, including SAEs, on the CRF regardless of the severity or relationship to study treatment.
- Determine the seriousness, relationship, and severity of each event.
- Determine the onset and resolution dates of each event.
- Monitor and record all pregnancies in female subjects and follow up on the outcome of all pregnancies.
- Complete an SAE form for each SAE and fax or email it to the Sponsor within 24 hours of the study site staff becoming aware of the event.
- Pursue SAE follow-up information actively and persistently. Follow-up information must be reported to the Sponsor within 24 hours of the study site staff becoming aware of new information.
- Ensure all AE and SAE reports are supported by documentation in the subjects' medical records.
- Pursue AE follow-up information, if possible, until the event has resolved or become stable. Record AE follow-up information, including resolution, on the CRF, as applicable.
- Report SAEs to local ethics committees, as required by local law.

15.6.2. The Sponsor

The Sponsor's responsibilities include the following:

- Before a site can enroll any subjects, the Clinical Monitor is responsible for reviewing with study site staff the definitions of AE and SAE, as well as the instructions for monitoring, recording, and reporting AEs and SAEs.
- The Sponsor is to notify all appropriate regulatory authorities, central ethics committees, and Investigators of SAEs, as required by local law, within required time frames.

CONFIDENTIAL

The information contained herein may not be used, disclosed, or published without the written consent of
Biogen MA Inc.

16. STATISTICAL METHODS AND DETERMINATION OF SAMPLE SIZE

The objectives of the study and the endpoints to be analyzed are listed in Section 6.

16.1. Demography and Baseline Characteristics

Demographics and baseline data will be summarized by treatment group with summary statistics (mean, standard deviation [SD], median, and range) or with frequency distributions.

16.2. Efficacy

16.2.1. Analysis Population

The modified intent-to-treat (MITT) population, defined as all subjects who are randomized and receive at least 1 dose of study treatment, will be used for the efficacy analyses unless otherwise specified. For each endpoint, additional conditions may apply to the definition of the population for the analysis. Subjects will be analyzed in the groups to which they were randomized.

The per-protocol (PP) population, defined as all subjects who are randomized and without major protocol violations, will be used for sensitivity analysis for the primary endpoint.

Subgroup analysis (e.g., background therapy strata as subgroup) will be done for the primary endpoint and some of the secondary endpoints. The details will be specified in the SAP.

16.2.2. Methods of Analysis

16.2.2.1. General Considerations

Summary statistics will be presented. For continuous endpoints, summary statistics will generally include: number of subjects with data, mean, standard deviation, median, and range. For categorical endpoints, this will generally include number of subjects randomized, number of subjects with data, and percentage of subjects with data in each category. Statistical testing for efficacy endpoints will be made between subjects treated with BG00011 and with placebo.

All statistical tests will be 2-sided.

16.2.2.2. Analysis of the Primary Endpoint

The population for the primary endpoint analysis will be subjects in the MITT population with a baseline and at least 1 postbaseline FVC measurement.

The primary efficacy outcome variable is the yearly rate of change in FVC (actual value, expressed in mL, over 52 weeks). The primary endpoint will be analyzed using a random coefficients linear regression model, with an absolute change in FVC as the outcome variable

CONFIDENTIAL

The information contained herein may not be used, disclosed, or published without the written consent of Biogen MA Inc.

assuming linear decline in lung function over time. The model includes random coefficients for intercept and slope (time), and fixed-effect terms for treatment, randomization stratum (background therapy), age, and baseline FVC. Interaction terms in the model will be the interaction between treatment and time, and the interaction between pirfenidone or nintedanib and time.

Every effort should be made to reduce the amount of missing data. In the analysis of the primary endpoint, missing data will be assumed to be missing at random. An unstructured variance-covariance structure will be used to model the within-patient measurements variability. If it fails to converge, an AR(1) structure will be used. The variance-covariance matrix, modeled to estimate the interindividual variability, is considered to have a variance components structure. Because the statistical model assumes a linear decline in lung function over time and, hence, implicitly imputes missing data based on individual's estimated rate of worsening of lung function prior to treatment discontinuation, similar to linear extrapolation. If a subject who was not on background therapy at randomization initiates treatment with background therapy during the study, the subject's data collected after the initiation of background therapy will be excluded from the primary analysis. However, a sensitivity analysis that includes the excluded data will be performed.

Support analyses for the primary endpoint includes:

1. Analysis using multiple imputation with pattern mixture models will be carried out. Details of sensitivity analysis and assumptions for different pattern will be described in the statistical analysis plan (SAP).
2. A mixed model of repeated measures model will be used to compare the difference between the 2 treatment groups in FVC change at 52 weeks and other scheduled visits. An unstructured variance-covariance structure will be used in this model. If the model fails to converge, an AR(1) structure will be used.
3. Rate of decline in percent predicted FVC at 52 weeks will be analyzed by the same method as FVC actual value.

A model including the interaction between treatment and background therapy strata will be used to explore the treatment effects within each subgroup.

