16.9. Sample Size Considerations

The sample size calculation is based on the annual declining rate in FVC (mL/year). With 145 subjects randomized per arm, and assuming a 15% dropout rate over a 1-year treatment period, the study has approximately 80% power to show that the BG00011 treatment arms differentiate from the arm without BG00011 at a 2-sided 15% α level, given a treatment effect of 82.5 mL/year with a common standard deviation of 280 mL. The calculation is based on the assumption that the FVC decline rate in subjects receiving placebo and no background therapy is 220 mL/year, and in subjects receiving background but no BG00011 therapy it is assumed to be 110 mL/year. A 60% reduction in the FVC decline rate in the subjects receiving placebo would be a treatment effect of 132 mL/year. A 30% reduction in the FVC decline rate in subjects receiving background therapy would be a treatment effect of 33 mL/year. With the assumption that 50% of each type of subject are randomized in the study, the combined treatment effect is approximately 82.5 mL/year. The 15% dropout rate for this study was estimated based on prior experience for the placebo arms in the Phase 3 studies for nintedanib and pirfenidone [King 2014; Richeldi 2014].

CONFIDENTIAL

The information contained herein may not be used, disclosed, or published without the written consent of Biogen MA Inc.

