7.2 Analysis of Primary Endpoint

7.2.1 Primary Analysis

The estimand of the primary analysis is the mean difference of the change from baseline in FVC (expressed in mL, at each week 26 or week 38) between treatment and placebo group in the MITT population [[ICH E9 \(R1\) Addendum 2014, 2017](#)]. Data will be censored when subject experienced intercurrent event (i.e. death and/or lung transplantation and/or treatment discontinuation) and prematurely discontinued the study treatment. The estimate of this analysis reflects the treatment effect of BG00011 if the drug were taken as directed [de jure efficacy estimand].

Due to the study early termination, the estimand will assess the mean difference of the change from baseline in FVC (mL) at week 26 and 38 based on the data availability and visit times of interest. Both change from baseline in FVC (mL) at weeks 26 and 38 are the continuous secondary efficacy endpoints. If less than 20 subjects (i.e. <20 subjects) had non-missing measurements at either visit time of interest, the mean difference comparison will not be performed at that visit time due to the insufficient data.

A random coefficients linear regression model will be used as the primary analysis where the change from baseline in FVC (mL) is the outcome variable assuming linear decline in lung function over time. The model will include random coefficients for intercept and slope (time), and fixed-effect terms for treatment, randomization stratum (background therapy), age, and baseline FVC along with treatment-by-time interaction and background therapy status-by-time interaction. In this model, time is considered as a continuous variable.

An unstructured variance covariance structure will be used to model the within-patient measurements variability. If the unstructured covariance structure matrix results in a lack of convergence, first-order autoregressive, AR(1), covariance structure will be used. The Kenward-Roger approximation will be used to estimate the denominator degrees of freedom.

If a subject who experiences unscheduled visit(s) for acute exacerbation of IPF and has non-missing FVC measurement(s), those unscheduled FVC measurement(s) will be included in the primary analysis.

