7.2.2 Supplementary Analysis

A mixed model of repeated measures (MMRM) model will be used as supplementary analyses to analyse the change from baseline in FVC using the same fixed effects, for treatment, randomization stratum (background therapy), age, and baseline FVC along with treatment-by-time interaction and background therapy status-by-time interaction, as in the random coefficients linear regression model. MMRM assume a nonlinear decline in lung function over time. An unstructured variance covariance structure, same as used in the primary analysis, will be used to model the within-patient measurements variability. If the unstructured covariance structure matrix results in a lack of convergence, first-order autoregressive, AR(1), covariance structure will be used. The Kenward-Roger approximation will be used to estimate the denominator degrees of freedom.

The comparison will be conducted to evaluate the treatment difference in absolute FVC at week 26 and 38 between BG0011 cohort versus placebo cohort, respectively.

- If a subject who experiences unscheduled visit(s) for acute exacerbation of IPF and has non-missing FVC measurement(s), such unscheduled FVC measurement(s) may be included in the analysis by using the follow rule.
- If the unscheduled FVC measurement is between 2 consecutives post-baseline scheduled visits with both FVC measurements non-missing, the unscheduled FVC measurement(s) will not be included in the model. If more than one unscheduled FVC measurements are between the same visit window (between the same 2 consecutives post-baseline scheduled visits), all unscheduled FVC measurements will not be included in the model.
- If the unscheduled FVC measurement is between 2 consecutives post-baseline scheduled visits with one of the two FVC measurements missing, the unscheduled FVC measurement will be included in the model and imputed as the schedule visit with missing FVC value. If more than one unscheduled FVC measurements are between the same visit window, the unscheduled FVC measurement which is closest to the scheduled visit with missing FVC measurement will be included in the model and imputed as the schedule visit with missing FVC value.

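### The FVC models adjust the level of FVC change for age and baseline FVC but not the rate of decline; adding by-time terms is a nearly free gain in precision

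*Protocol*

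**What the plan says.** Protocol 16.2.2.2, with the same wording in Versions 1 and 2, analyses the yearly rate of change in FVC with a random intercept and slope model. The covariates enter as "fixed-effect terms for treatment, randomization stratum (background therapy), age, and baseline FVC". The by-time terms are then listed: "Interaction terms in the model will be the interaction between treatment and time, and the interaction between pirfenidone or nintedanib and time".

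SAP section 1 states that the SAP was developed from protocol Version 1, that Version 2 was not implemented, and that the SAP overrides the protocol's statistical considerations. The operative text is therefore SAP 7.2.1. There "the change from baseline in FVC (mL) is the outcome variable assuming linear decline in lung function over time", and the fixed effects again end with "age, and baseline FVC along with treatment-by-time interaction and background therapy status-by-time interaction". Because the study stopped early, the treatment comparison is made at Weeks 26 and 38.

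The MMRM in SAP 7.2.2 is fitted "using the same fixed effects, for treatment, randomization stratum (background therapy), age, and baseline FVC along with treatment-by-time interaction" and background therapy-by-time. The complementary analysis in SAP 7.2.3 reuses the 7.2.1 model on data that include observations after discontinuation. SAP 7.3.1.1 applies all three analyses to percent predicted FVC.

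On incomplete data, the protocol says "missing data will be assumed to be missing at random". SAP 7.2.1 makes the same assumption and censors data after death, transplantation or treatment discontinuation. No analysis in the unredacted text gives age or baseline FVC a by-time term.

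**The concern.** A main effect in a slope model moves a subject's whole line up or down by a constant. It cannot account for subjects with different baseline FVC or age declining at different rates. Since the outcome is already change from baseline, the planned adjustment acts where there is little to adjust and misses the quantity of interest. The plan does give background therapy a by-time term, so it recognises that a prognostic factor can act on the slope.

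Two things could be at stake. The first is precision: slope variation that baseline FVC could explain stays in the random slope. The second is the missing-at-random argument. It protects the estimate only if the mean model given the observed covariates is adequate. A subject with few visits is pulled towards a mean slope that ignores baseline FVC. In a study stopped for a safety imbalance, discontinuation that differs by arm and by severity is conceivable.

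**Working it through.** **1. What the terms do.** For subject *i* at time *t*, the planned model is

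change = β0 + β1·treatment + β2·stratum + β3·age + β4·FVC₀ + (γ0 + γ1·treatment + γ2·stratum)·*t* + aᵢ + bᵢ·*t* + error.

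The treatment difference at time *t* is β1 + γ1·*t*. Baseline FVC contributes β4·FVC₀ at every visit, the same at Week 4 as at Week 38. If the true slope changes by *g* mL/year per SD of FVC₀, that part falls into the random slope bᵢ and adds *g*² to its variance. In the MMRM, a single baseline coefficient is imposed on all visits.

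**2. The plan's own power.** Inputs are from protocol 16.9 and SAP section 4: "With 145 subjects randomized per arm", 15% dropout, effect 82.5 mL/year, SD 280 mL, two-sided alpha 0.15.

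- Evaluable per arm: 145 × 0.85 = 123.25.
- SE = 280 × √(2/123.25) = 35.67 mL/year.
- 82.5/35.67 = 2.313; 2.313 − 1.440 = 0.873; power = 80.9%. The stated figure of about 80% is reproduced.

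**3. Precision on the planned 52-week slope.** Let ρ be the correlation between baseline FVC and individual slope. It is not in the documents, so a range is shown. Adjusting the slope replaces 280 by 280·√(1 − ρ²).

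| assumed ρ | variance removed | SD (mL) | power |
|---|---|---|---|
| 0.1 | 1% | 278.6 | 81.2% |
| 0.2 | 4% | 274.3 | 82.2% |
| 0.3 | 9% | 267.1 | 83.8% |
| 0.4 | 16% | 256.6 | 86.1% |

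The fall in SE by this formula is 1 − √(1 − ρ²): 2.0% at ρ = 0.2 and 8.3% at ρ = 0.4. A simulation (assumed slope SD 250 mL/year, residual SD 100 mL) confirms that main effects alone do nothing for the slope. Its SE was 33.1 with or without them at ρ = 0.2, and 35.9 with or without them at ρ = 0.4. With the by-time term it was 32.7 and 33.1.

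**4. Precision at the SAP's visits.** The planned effect corresponds to 82.5 × 26/52 = 41.3 mL at Week 26 and 82.5 × 38/52 = 60.3 mL at Week 38. Less time has elapsed and measurement error is not reduced, so the gain is smaller: about 1 to 6% of the SE for ρ of 0.2 to 0.4, depending on the assumed error. One set of runs (145 per arm, residual and baseline error 100 mL each) gave, at Week 26, 19.0 to 18.8 mL (1%) at ρ = 0.2 and 19.4 to 18.9 mL (3%) at ρ = 0.4.

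**5. Bias in the treatment difference.** Large-sample fits used the protocol's visit times, with these assumptions: *g* = 50 or 100 mL/year per SD; random-slope SD 260, intercept SD 60 and residual SD 100 mL. Dropout was 15 to 16% per arm, except for one scenario with 30% on BG00011.

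- *Same dropout relation to baseline FVC in both arms.* Adding the term changes the treatment difference by less than 0.5 mL/year. Each arm's slope is off without the term (placebo by about 3.5 to 11 mL/year), but the errors cancel.
- *Relation differs by arm.* The difference is off by 3.2 to 6.6 mL/year (*g* = 50) or 6.1 to 12.9 mL/year (*g* = 100), which is 4–8% or 7–16% of 82.5. The term removes this.

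For Weeks 26 and 38, a harsher scenario was used: 30% of BG00011 subjects below median baseline FVC leave by Week 16, and none on placebo do. With main effects only, at ρ = 0.2 and 0.3:

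| visit | truth | estimates | excess | SE |
|---|---|---|---|---|
| Week 26 | 41.3 | 42.6, 44.1 | 1.4 to 2.9 | about 20 |
| Week 38 | 60.3 | 62.8, 65.2 | 2.5 to 4.9 | about 26 |

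A large-sample run with different error assumptions gave 63.5 and 66.4 at Week 38 (excess 3.2 and 6.1), and 59.7 and 60.7 with the by-time term. About 2 to 4 mL is a fair summary; single runs ranged from 1.4 to 6.1 mL.

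**The case against.** The strongest reply is that this is a modelling preference. The model is stated consistently across documents. Randomization balances baseline FVC in expectation. SAP 6.7 makes all inference nominal, and the study had already stopped. The 52-week power figures describe an analysis that will not be run. At the SAP's visits the gain is small, and even in a scenario built to produce bias the excess is below 0.2 SE (2.9/20 = 0.15; 4.9/26 = 0.19). The documents give neither the size nor the sign of the correlation, and no dropout figures by arm or by baseline FVC. Nothing was calculated for age. All of this stands, and it limits the size of the point.

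It can also be said that subjects who stop treatment are to complete remaining visits, and that SAP 7.2.3 uses those data. That limits differential dropout, but 7.2.3 is fitted with the same model and so does not supply the missing adjustment.

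A reader might infer two stronger things. One is that the slope comparison is unadjusted. It is not: background therapy, the randomization stratum, has its own by-time term, and only age and baseline FVC lack one. The other is that dropout depending on baseline FVC is enough to bias the comparison. Step 5 shows that it is not when the dependence is the same in both arms.

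**Conclusion.** This is a low-cost improvement, not an error. The planned adjustment for age and baseline FVC does not reach the rate of decline, in either protocol version or in any of the three unredacted SAP analyses of FVC.

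The expected cost is modest lost precision, conditional on decline depending on baseline FVC: about 1 to 6% of the SE at Weeks 26 and 38 for assumed ρ of 0.2 to 0.4. Bias requires that dependence and also a dropout relation that differs by arm. It is then about 2 to 4 mL in an assumed scenario, small against the sampling error. The early stop makes differential discontinuation plausible, but the documents do not show that it occurred.

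These statements assume a treatment effect that does not vary with baseline FVC; that case was not examined. The benefit of an age-by-time term is not quantified. The sample size calculation is unaffected.

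**What to change.** - In SAP 7.2.1, and so in 7.2.3, add baseline FVC-by-time and age-by-time as fixed effects in the random coefficients model.
- In the SAP 7.2.2 MMRM, add baseline FVC-by-visit.
- For percent predicted FVC (SAP 7.3.1.1), use baseline percent predicted FVC in the same way.

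If the sponsor prefers to keep the stated primary model, the same terms can be run as a prespecified sensitivity analysis.

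The cost is a line or two of SAP text and no new data, since both covariates are already collected and in the model. It takes two fixed-effect degrees of freedom in the random coefficients model. In the MMRM it takes nine, if all ten post-baseline spirometry visits are modelled (ten baseline coefficients in place of one). SAP 1.1 has the plan finalized before the Part I data lock and provides for documented revisions. The change should be made before that lock to count as prespecified.
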